6.14.3 Change in imaging modality

Magnetic resonance imaging (MRI) may be used in lieu of CT, and PET/MRI in lieu of PET/CT for patients with contraindications to the administration of contrast agents, or due to other medical reasons, at the same time points as CT, or in addition to CT, at the discretion of the investigator (in this case, MRI may be performed as/when appropriate). The method used at baseline should be used throughout the study unless otherwise medically indicated.

7. STATISTICAL METHODOLOGY

7.1 General principles of statistical programming

The statistical analysis will be performed on the analysis study database with appropriate software, SAS® Software version 9.4 or above (SAS Institute, Cary, N.C.).

7.2 Variable types and descriptive statistics

Descriptive statistics will be calculated using as reference the number of patients in the relevant analysis population (any exception will be specified) according to the nature of the data as follows:

Continuous variables (e.g. age, body weight): number of non-missing observations, arithmetic mean, standard deviation (StD), minimum and maximum values, quartiles (median, Q1 and Q3).

If there are less than 5 observations, only the number of non-missing observations, arithmetic mean, median, minimum and maximum will be presented.

Descriptive statistics of plasma concentrations and PK parameters will include n, arithmetic mean, geometric mean, StD, median, coefficient of variation CV (%), geometric CV (%), minimum and maximum. Geometric mean and the geometric CV (%) will be derived from non-zero values. For plasma concentrations, the number of non-zero values (m) will also be reported.

Categorical variables: (e.g. ECOG, ethnicity) Number of non-missing observations, the number of missing and the relevant percentage on the analysis population, number and relative frequencies. If not defined otherwise, the percentage denominator will be the number of patients with non-missing information.

In case of subcategories, the relative frequencies will be calculated on the basis of the patients in the respective category, in this case a footnote will be added explaining the different denominators.

Time variables (durations): Will be summarized using arithmetic mean, StD, minimum and maximum values, median and quartiles (Q1, Q3) and will be presented in months (unless otherwise stated).

Time to event variables: (PFS, OS, etc.) Unless otherwise stated, Kaplan Meier estimates of Q1, Median, and Q3 along with their 95% Confidence Intervals will be presented.

The majority of data obtained on the eCRF and entered into the database will be provided in separate data listings showing individual patient values. The planning and reporting of statistical analyses will be carried out as described in the [REDACTED] standard operating procedures (SOPs).

Any patient who withdraws from the study will be analyzed with the data available. Imputation of missing values will not be performed, unless specified in the relevant sections of the SAP.

7.3 Convention on missing data

For the statistical analysis, some particular data handling conventions (handling of missing data, pooling of centers) are planned. The details are present in the respective sections.

7.4 Data included in the analysis and cut-off date

All the analyses mentioned in Sections 8 to 16 will be performed using data collected in the database up to the data cut-off date. A cut-off date will be defined for each of these analyses and will be specified in the outputs.

Of all the termination dates of the patients included in the final analysis, the last termination visit date will be defined as the cut-off date and will be specified in the outputs.

Analyses will be based on the data collected for patients who did not fail screening, and for all patients treated prior to or on the cut-off date.

Any data collected beyond the cut-off date will not be included in the analysis. Only data with an assessment date or event start date (e.g. vital sign assessment date or start date of an adverse event) prior to or on the cut-off date will be included in the analysis. For example, if the cut-off date is 15JUN2017 then an AE starting on 13JUN2017 will be reported, whereas an AE with start date on 17JUN2017 will not be reported.

All events with an event start date either before or on the cut-off date and an event end date after the cut-off date will be reported as "continuing at the cut-off date". The same rule will be applied to events starting either before or on the cut-off date and not having a documented end date. This approach applies, in particular, to adverse event and concomitant medication reports. For these events, the end date will not be imputed and therefore will appear as missing in listings.

If it is required to impute an end date to be able to perform a specific analysis (e.g. end date after the cut-off date) the cut-off date needs to be imputed as an end date. The imputed date will be displayed and flagged in the listings.

Any data collected beyond a patient's withdrawal of consent will not be included in the analysis; except for SAEs and the date of death provided confirmed by a public registry and patient status entered after the date of withdrawal of consent e.g. end of treatment, end of post-treatment follow-up.

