8.2 Adverse Event and Serious Adverse Event Recording and Reporting

All AEs (except non-serious AEs for screening failures) that occur after the provision of informed consent and up to 30 days after last study drug administration will be recorded in the eCRF and in the patient’s medical records, whether or not they are considered by the investigator to be related to the study drug. Thereafter, only AEs assessed as related should be recorded. All AEs should be recorded using acceptable diagnoses, if possible. For screening failure patients, non-serious AEs will not be recorded in the eCRF but only in the patient’s medical records.

In addition, all SAEs and AEs of special interest will be recorded on the SAE report form. Study centres and investigators are instructed to report all SAEs and AEs of special interest to the contract research organisation (CRO) mentioned below within 24 hours using the study-specific- SAE report form. Preferably, the diagnosis instead of the individual symptoms should be reported. For overdoses, the diagnosis and if applicable the accompanying symptoms caused by the overdose should be reported.

If an AE has already been reported, it is not necessary to report each individual sign and symptom of that AE as a separate AE. For example, if a myocardial infarction is reported as an AE, there is no need to report elevated creatine phosphokinase and abnormal ECG, or other related signs,

symptoms, or laboratory values as separate AEs. However, if such events occur in isolation, and myocardial infarction is not diagnosed, then each event should be reported as an AE.

[figure not shown]
All non-serious AEs must be followed up for a final outcome. An outcome of “unknown” is not considered to be an acceptable final outcome. An outcome of “not yet resolved” is an acceptable final outcome for non-serious AEs at the end of a patient’s participation in a study. All SAEs must be followed up for a final outcome until resolution or, if resolution becomes unlikely, until stabilisation or death. The follow-up for SAEs that are a progression of DLBCL only until the end of a patient’s participation in a study is acceptable. This includes obtaining information on recovery and any sequelae and, in the case of a fatal outcome, the cause of death.

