16.5.2 Patients who reduced the daily prescribed LEN dose

Incidence and frequency of TEAEs by the degree of LEN dose reduction

TEAEs will be tabulated by SOC, PT, and NCI-CTCAE Grade as described in Section 10.7 for the following subgroups of patients:

- Patients with no reduction of LEN.
- Patients with a minimum LEN dose of 20 mg/day: for this category, all TEAEs that occurred *before* exceeding the threshold of 20 mg/day are considered. The calculation of incidence rates is based on the number of patients in the SAF.
- Patients with a minimum LEN dose of <20 mg/day but ≥5mg/day: for this category, all TEAEs are considered that happened *after* exceeding the threshold of 20 mg/day. The calculation of incidence rates is based on the number of patients who had a reduction to <20 mg/day but ≥5mg/day.

Duration of TEAEs of interest

The duration of various TEAEs of interest will be summarized for the following dose categories:

- Patients who are treated with 25 mg LEN per day
- Patients who are treated with 20 or 15 or 10 or 5 mg LEN per day
- Patients who are treated with 15 or 10 or 5 mg LEN per day

For each category only those TEAEs are considered that happen *during* the period of treatment with the particular dose or dose range defining the categories above (e.g., only those TEAEs are considered that happen during while the patient is on 15 or 10 or 5 mg LEN per day). The duration of a particular TEAE is summarized for the following TEAEs:

- Neutropenia ≥G3 (PT 'neutropenia')
- Thrombocytopenia ≥G3 (PT 'thrombocytopenia')
- Infections and infestations ≥G3 (SOC 'infections and infestations')
- Infective pneumonia ≥G3 (SMQ code 20000231, narrow scope)
- Urinary tract infection ≥G3 (CMQ as defined in the SAP Appendix)

-
- Sepsis \geq G3 (CMQ as defined in the SAP Appendix)
 - Febrile neutropenia (PT 'febrile neutropenia')
 - Thromboembolic events of all CTCAE Grades (SMQ code 20000081)
 - Thromboembolic events \geq G3 (SMQ code 20000081)

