20.12 TEAEs leading to study drug modifications

Based on the SAF, TEAEs leading to any Study Drug Modification of MOR00208 or LEN regardless of any study drug relationship by Primary SOC, PT and NCI-CTCAE Grade will be tabulated. TEAEs leading to the following modifications will be reported separately by modification category:

- Any modification (interruption or dose reduction)
- Interruptions
- Dose reductions (only applicable for LEN)

The TEAEs leading to the modifications mentioned above will be reported separately for:

- MOR00208
- LEN
- Any study drug

A Listing will be provided displaying TEAEs leading to study drug modifications (SAF).

20.13 Time to onset of individual TEAEs, duration of individual TEAEs, and cumulative duration of TEAEs per cumulative exposure to tafasitamab

For the categories listed below in this section, the following will be summarized based on the SAF:

- Time to TEAE onset [in days]
- TEAE duration [in days]
- Cumulative duration of TEAEs per cumulative exposure to MOR00208 [in months]
 - The cumulative duration of TEAEs will be reported in months
 - The cumulative exposure to MOR00208 will be calculated in years:
[(end date of the MOR00208) – (start date of MOR00208) + 1] / 365.25.

The summaries will be provided for the following categories:

- PT Neutropenia (all Grades)
- PT Neutropenia (\geq Grade 3)
- PT Thrombocytopenia (all Grades)
- PT Thrombocytopenia (\geq Grade 3)

STATISTICAL ANALYSIS PLAN

MorphoSys AG
MOR208C203

-
- SOC Infections and infestations (all Grades)
 - SOC Infections and infestations (\geq Grade 3)
 - SMQ "Infective pneumonia" (all Grades)
 - SMQ "Infective pneumonia" (\geq Grade 3)
 - CMQ "Urinary tract infection" (all Grades)
 - CMQ "Urinary tract infection" (\geq Grade 3)
 - CMQ "Sepsis" (all Grades)
 - CMQ "Sepsis" (\geq Grade 3)
 - CMQ "Opportunistic infections" (all Grades)
 - CMQ "Opportunistic infections" (\geq Grade 3)
 - PT Fatigue + PT Asthenia (all Grades)
 - All PTs including the verbatim Diarrhoea (all Grades)
 - PT Nausea + PT Vomiting (all Grades)
 - PT Febrile neutropenia (all Grades)
 - SMQ Thromboembolic event (all Grades)
 - SMQ Thromboembolic event (\geq Grade 3)

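### Where a TEAE duration analysis needs an end date, SAP 7.4 imputes the common data cut-off with no cap at death or study exit, and 20.13 has no rule for open events

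*SAP*

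**What the plan says.** SAP 7.4 sets a default and an exception. The default covers events that end after the cut-off or have no documented end: "For these events, the end date will not be imputed and therefore will appear as missing in listings". The exception begins "If it is required to impute an end date to be able to perform a specific analysis"; in that case "the cut-off date needs to be imputed as an end date", and the imputed date is shown and flagged in the listings. At the final analysis the cut-off is one date for everyone: "the last termination visit date will be defined as the cut-off date". The section opens with its scope: "All the analyses mentioned in Sections 8 to 16 will be performed using data collected in the database up to the data cut-off date".

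Two parts of the SAP analyse TEAE duration.

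- Section 16.5.2, by lenalidomide dose category: "The duration of a particular TEAE is summarized for the following TEAEs", followed by a list that includes grade 3 or higher neutropenia, thrombocytopenia and infections.
- Section 20.13, for a longer list: time to onset, duration, and "Cumulative duration of TEAEs per cumulative exposure to MOR00208 [in months". Its denominator runs from the MOR00208 start date to the MOR00208 end date, in years.

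Open events are foreseen. Protocol 8.2 states that an unresolved status "is an acceptable final outcome for non-serious AEs at the end of a" patient's participation.

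**The concern.** A duration cannot be computed without an end date, so a duration summary is the natural trigger for the exception in 7.4. The date it supplies is common to the whole study. It takes no account of whether the patient was alive, in contact or still in the study. A patient who died or left early with an open event would be credited with event time up to the cut-off.

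The SAP handles exposure differently: section 8.9.2 truncates the MOR00208 exposure interval at death, and the 20.13 denominator stops with MOR00208. Numerator and denominator of the 20.13 ratio could therefore cover very different periods.

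At stake are the mean, standard deviation, maximum and cumulative duration of the listed toxicities. These are descriptive, but they would be read as evidence of how long toxicity lasts.

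**Working it through.** The plan gives no figure on this point, so there is none to reproduce. The check is which rule applies where, then date arithmetic.

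**Which rule applies**

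- 16.5.2: inside Sections 8 to 16, so the exception in 7.4 is available and is the only imputation rule offered.
- 20.13: outside that stated scope and silent. If 7.4 is carried over, open events run to the cut-off. If the general rule in 7.2 applies (no imputation unless specified), open events drop out.

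**Inputs**

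- Duration = end − start + 1 day. This is assumed for TEAEs; the SAP uses this form for time-to-event variables (6.9) and exposure (8.9.2).
- Month = 30.4375 days and year = 365.25 days (SAP 6.6).
- Cut-off at study day 365, 1,096 or 1,826 (assumed). Day 365 is roughly the last-enrolled patient at the primary analysis, about 12 months after last enrolment (SAP 5.4.2). Day 1,826 is 5 years, the per-patient study duration in Protocol 5.3.2. An earlier-enrolled patient has a later cut-off day.
- Example patient (assumed): onset day 40, last MOR00208 and death on day 60, event not resolved.

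**One patient**

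Capped at death: 60 − 40 + 1 = 21 days.

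| Cut-off day | Duration with cut-off imputed |
|---|---|
| 365 | 365 − 40 + 1 = 326 days |
| 1,096 | 1,096 − 40 + 1 = 1,057 days |
| 1,826 | 1,826 − 40 + 1 = 1,787 days |

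**The 20.13 ratio for that patient**

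With duration d and exposure e in days, months of TEAE per year of exposure = (d / 30.4375) / (e / 365.25) = 12 × d / e. Here e = 60.

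- Capped: 12 × 21 / 60 = 4.2.
- Run to day 1,826: 12 × 1,787 / 60 = 357.4.

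One continuous event confined to the exposure period cannot exceed 12.

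**Mean over many events**

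Let resolved events average 20 days and a share f be open, each with duration D (both assumed). Mean = (1 − f) × 20 + f × D. For f = 5% and D = 1,787: 0.95 × 20 + 0.05 × 1,787 = 108.35.

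| Share open | Capped, D = 21 | D = 326 | D = 1,057 | D = 1,787 |
|---|---|---|---|---|
| 0% | 20 | 20 | 20 | 20 |
| 5% | 20.1 | 35.3 | 71.9 | 108 |
| 10% | 20.1 | 50.6 | 124 | 197 |
| 20% | 20.2 | 81.2 | 227 | 373 |

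For a fixed number of events the cumulative sum is multiplied by the same factor. In the last column that is 108.35 / 20.05 = 5.4, 196.7 / 20.1 = 9.8 and 373.4 / 20.2 = 18.5. With fewer than half the events open, the median stays within the range of the resolved durations.

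**If open events drop out of 20.13 instead**

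The numerator loses f × 21 out of (1 − f) × 20 + f × 21. That is 1.05 / 20.05 = 5%, 2.1 / 20.1 = 10% or 4.2 / 20.2 = 21% of cumulative duration, and more if open events last longer than 21 days. The denominator still counts those patients' exposure.

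**The case against.** The strongest reply is that the default in 7.4 is no imputation, and that neither 16.5.2 nor 20.13 asks for an imputed end date. A summary of events with recorded end dates would also fit the text. A reader might infer that every adverse event without an end date receives the cut-off; the documents do not support that. Imputation is conditional, and applying it to 20.13 is an inference because 7.4 names Sections 8 to 16. This stands and limits the claim. It does not remove it: dropping open events is also biased, in the other direction, and the only end date the SAP offers is the uncapped cut-off.

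Other parts of the reply also stand.

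- The documents do not say how end dates are recorded at death, and Protocol 8.2 follows serious events to resolution, stabilisation or death. How many events stay open is unknown.
- Safety objective 7 concerns frequency and severity. Duration is an additional descriptive summary, medians and quartiles are reported too, and imputed dates are flagged.
- Cumulative duration longer than the time patients were alive is not in itself an error, since overlapping events in a pooled category can produce it.

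**Conclusion.** The point holds in limited form. Following 7.4 as written in a duration analysis can credit a patient who has died or left with years of event time: 1,787 days instead of 21 in the example. For 16.5.2 this follows from the stated scope. For 20.13 the plan is silent, and both available readings bias the result.

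The size rests on two unknowns, the share of open events and the distance to the cut-off. With none open there is no effect. With 5% to 20% open and resolved events averaging 20 days, the mean rises from about 20 days to between 35 and 81 days at a day-365 cut-off, and to between 108 and 373 days at day 1,826. Maxima and cumulative sums are distorted in the same direction.

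A reader might go further and call the cumulative-duration ratio meaningless. That is not supported: the distortion depends on a share the documents do not give. Medians are little affected when few events are open. Incidence and time to onset do not use the end date, and the primary response-rate analysis is untouched.

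**What to change.** In SAP 7.4, 16.5.2 and 20.13, state that for duration analyses only an open TEAE ends at the earliest of death, date of last contact (already derived in 6.10) or study discontinuation, and data cut-off. Flag these events and report their number by category. In 20.13, use this capped end date and restrict the TEAE time and the MOR00208 exposure to the same time window.

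Do not cap at last dose plus 30 days. SAP 10.7.3 counts related events that start later than that as TEAEs, so the end could precede the onset. Protocol 8.2 also follows events beyond that point.

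Optionally, add a Kaplan-Meier summary of duration with open events censored at the capped date, noting that death is a competing event.

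The cost is SAP wording and one derived date, with no new data. One limit remains: in telephone survival follow-up, Protocol 7.2.5 does not list general adverse event questions, so last contact can still lie beyond active observation. The flag and the count make that visible.

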7.5 Specifications and Analysis Database

Based on dataset in SDTM format provided by [REDACTED]'s Clinical Data Services group analysis datasets adhering to CDISC ADaM standard will be generated with SAS[®] software, version 9.4 or above, based on the soft lock of data for the main analysis or hard lock study database for the full final statistical analysis (after all the patients discontinue the study) and according to agreed Analysis Dataset Specifications (ADS).

7.6 Pooling of investigative sites

Data will be pooled from all investigative sites for the analyses. The justification for this is based on the following:

- The sites must implement one common protocol.
- The sponsor must provide close monitoring of study procedures and compliance.
- Several sites are expected to recruit a few patients only.
- The study sites must use common data collection procedures.
- For primary endpoint analysis the disease response assessments will be made centrally.

Geographical region, however, may be included as a factor in supportive and/or exploratory analyses, as well as safety analyses.

8. PATIENT DISPOSITION, BACKGROUND AND BASELINE CHARACTERISTICS

The number of patients screened, treated, progressed/relapsed, died, and those included in each analysis population will be summarized. In addition, patients will be listed and summarized who discontinue treatment during the combination phase (cycles 1 to 12), antibody monotherapy treatment phase (> cycle 12), or are being treated despite

progression, along with reasons for discontinuation. The number of patients followed up for overall survival will be summarized.

8.1 Screened patients

The number (%) of patients who were

- Screened
- Screen failure
- Enrolled

will be summarized by country, center, and overall. Percentages will be calculated based on the number of patients screened. In a separate summary the reason for screen failures will be presented.

8.2 Enrolled patients

The following summaries will be provided: % based on the total number of Enrolled patients:

- Number (%) of patients who were treated with study drug (split by MOR00208, LEN, and both study drugs).
- Number (%) of patients who are still on-treatment with study drug split MOR00208, LEN, both drugs, or any drug (all Cycles considered; only for the primary analysis).
- Number (%) of patients who are ongoing with combination treatment (Cycles 1-12).
- Number (%) of patients who discontinued *only* one of the two study drugs (split by LEN only, MOR00208 only), or *both* study drugs during combination treatment (Cycle 1 to 12) including the primary reason for discontinuation. The discontinuation of LEN as per protocol after Cycle 12 will not be considered here. If drugs are sequentially discontinued, the reason for discontinuation of the later drug will be reported as reason for the discontinuation of both drugs.
- Number (%) of patients who discontinued MOR00208 or LEN before completing 12 Cycles. All discontinuations are considered including both the discontinuation of MOR00208/LEN *only* or a sequential discontinuation of both drugs. The reason for discontinuation will also be reported.
- Number (%) of patients who *successfully* completed combination treatment (Cycles 1- 12), i.e., patients who completed 12 Cycles on *both* drugs.
- Number (%) of patients who reached Cycle 13 Day 1 on at least one study drug (split by both drugs, LEN only, MOR00208 only, any study drug).

**STATISTICAL ANALYSIS PLAN**MorphoSys AG
MOR208C203

-
- Number (%) of patients who are still ongoing with MOR00208 only, LEN only, or both drugs after completion of Cycle 12 (i.e., ongoing from Cycles 13 onwards; only for primary analysis).
 - Number (%) of patients who discontinued MOR00208 beyond Cycle 12 regardless of successful or unsuccessful completion of the combination treatment phase, including the reason for discontinuation.
 - Number (%) of patients who discontinued MOR00208 after *successful* completion of combination treatment phase (Cycle 1-12) including the reason for discontinuation. Successful completion means that the patient completed 12 Cycles on combination treatment.
 - Number (%) of patients who discontinued LEN after completion of the combination treatment (Cycle 1 to 12) including the reason for discontinuation (e.g., completion as per protocol).

NOTES:

- The following reasons for 'End of Treatment' as entered on the 'End of Treatment' eCRF page will be summarized under the term as "As per protocol":
 - "CYCLE COMPLETED - LAST DOSE OF LENALIDOMIDE ON AUG, 20TH 2017"
 - "AS PER PROTOCOL"
 - "PER PROTOCOL"
 - "TREATMENT COMPLETED PER PROTOCOL"
 - „ACCORDING TO PROTOCOL“
 - "IT WAS STOPPED AFTER 12 CYCLES PER PROTOCOL"
 - "PATIENT COMPLETED 12 CYCLES TREATMENT"
 - "COMPLETED"
 - "LEN TREATMENT COMPLETED"
- Patients are only treated with LEN for 12 Cycles as per protocol. However, patients who reached Cycle 13, and who are still on treatment with MOR00208 are not depicted on the 'End of Treatment' page as only patients who have undergone an 'End of Treatment Visit' will be represented on this page. To also consider LEN discontinuations 'as per protocol' for patients who are still ongoing with MOR00208 treatment the following strategy will be applied:

Patients who reached Cycle 13 and who are not already represented on the 'End of Treatment' page will also be reported as having discontinued LEN. The reason for discontinuation will be reported as "As per protocol" if there is no evidence from

**STATISTICAL ANALYSIS PLAN**MorphoSys AG
MOR208C203

the recorded adverse events that a patient has discontinued LEN due to an adverse event, i.e. action taken with LEN for the respective event is recorded as 'Study drug permanently discontinued due to this AE. In the latter case the reason for discontinuation will be reported as "Adverse Event".

- Number (%) of patients who discontinued LEN at any time during the study including the reason for discontinuation.
- Number (%) of patients who discontinued MOR00208 at any time during the study including the reason for discontinuation.
- Number (%) of patients who discontinued LEN at any time during the study without discontinuation of MOR00208 at the same time including the reason for discontinuation.
- Number (%) of patients who discontinued MOR00208 at any time during the study without discontinuation of MOR00208 at the same time including the reason for discontinuation.

Listings showing the reason for being eligible based on inclusion and exclusion criteria will be shown. Another listing depicting information on patient disposition will be prepared.

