6.6.2 Management of Toxicities

The next cycle of treatment may begin on the scheduled Day 1 if:

- ANC is $\geq 1.000/\text{mm}^3$ (unless neutropenia is due to infiltration of bone marrow)
- Platelets $\geq 50000/\text{mm}^3$ (unless thrombocytopenia is due to infiltration of bone marrow, patient may have received transfusion) and absence of active bleeding
- No serious organ or other toxicity present.

If, based on medical judgment, the treating physician considers a change in laboratory parameter or AE not to be a study drug-related toxicity, but to represent a natural fluctuation in or progression of the underlying disease, then it is at the physician's discretion and assessment of the individual risk/benefit ratio to determine whether the patient should be dosed. The decision and rationale behind the decision should be documented in the source data.

If the above conditions are not met on Day 1 of a new cycle, the subject will be evaluated once every seven days and a new cycle will not be initiated until the toxicity has resolved as described above. Specific course of action for a given toxicity occurring in the course of the treatment cycle is described below.

If treatment needs to be interrupted for ≤ 28 days for the same study drug-related toxicity, the patient's treatment should continue, depending on the duration of treatment interruption, at the next protocol scheduled visit. No missed visits or doses of either drug should be made up.

If treatment with one study drug needs to be interrupted for >28 days for the same, persistent, drug-related toxicity, the study drug judged by the investigator to have caused the toxicity should be discontinued and the patient should continue to be dosed with the other study drug, as per protocol.

If treatment with both study drugs needs to be interrupted for >28 days for the same persistent study drug-related toxicity, judged by the investigator to be related to both study drugs (LEN and MOR00208), then the End of Treatment Visit will be performed and the patient will enter the follow-up phase (see [Section 5.3.1](#)).

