6.3.2 Date of last administration of study drug

The date of last administration of study drug (“last date of study drug”) is the last date when a non-zero dose of study drug is administered.

Last date of study drug is defined for each drug which is part of study treatment.

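### SAP 8.2 gives 'As per protocol' as the lenalidomide (LEN) stop reason at Cycle 13 without checking when LEN was last taken, so some early stops get the wrong reason before the final analysis

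*SAP*

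**What the plan says.** The notes in SAP 8.2 recognise a gap in the data. LEN is planned for 12 cycles. Of patients still on MOR00208 from Cycle 13 onwards, the SAP notes that they "are not depicted on the 'End of Treatment' page as only patients who have undergone an 'End of Treatment Visit' will be represented on this" form. It fills the gap by rule: "Patients who reached Cycle 13 and who are not already represented on the 'End of Treatment' page will also be reported as having discontinued LEN".

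A default then sets the reason: "The reason for discontinuation will be reported as 'As per protocol' if there is no evidence from". The evidence meant is any sign in "the recorded adverse events that a patient has discontinued LEN due to an adverse event", which the SAP specifies as an AE record whose action taken with LEN is permanent discontinuation. In that case the reason becomes *Adverse Event*.

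The same *As per protocol* label also collects free-text entries from the EOT page, among them "PATIENT COMPLETED 12 CYCLES TREATMENT" and the single word COMPLETED.

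The SAP has the data for a date check. Section 6.3.2 states: "Last date of study drug is defined for each drug which is part of study treatment". Section 8.9.6 takes LEN dosing start and stop dates from the Lenalidomide Dosing Record. The rule in 8.2 uses neither.

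**The concern.** A reader will take *As per protocol* to mean that LEN was given for the planned 12 cycles and then stopped. The rule infers this from two facts: the patient reached Cycle 13, and no AE carries the permanent-discontinuation action. Neither shows that LEN was still being taken near the end of Cycle 12, because both documents foresee patients continuing on MOR00208 alone after an earlier LEN stop.

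At stake is the table of reasons for stopping LEN. If early stops sit in the same row as planned stops, the table no longer shows why the combination was cut short. One patient's reported reason may also change between the primary and the final analysis, once an EOT page exists.

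**Working it through.** The plan gives no figure to reproduce. The check traces the rule for a patient who has reached Cycle 13, is still on MOR00208 and has no EOT page.

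| Route | Source | Does the AE exception apply? | Reason reported | Correct? |
|---|---|---|---|---|
| LEN taken through 12 cycles | Protocol 6.3 | No | As per protocol | Yes |
| Early stop; AE action is permanent discontinuation | SAP 8.2 | Yes | Adverse Event | Yes |
| LEN stopped at progression, MOR00208 continued | Protocol 6.3, 7.2.3 | No | As per protocol | No |
| Early stop by patient or investigator decision, or non-compliance | Protocol 6.9.1 | No | As per protocol | No |
| Early stop for toxicity; AE action left as temporary interruption | Protocol 6.6.2, 8.1 | No | As per protocol | No |

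**Progression.** This route is the best documented. Protocol 6.3 ends LEN at progression but lets the investigator continue MOR00208. Under Protocol 7.2.3 the cycle numbering then runs on and the EOT visit waits until the antibody is finally stopped. Such a patient can reach Cycle 13 with no EOT page. Protocol 8.2 keeps events clearly caused by progression out of the AE record, so progression itself cannot trigger the exception.

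**Toxicity.** After an interruption of more than 28 days for the same drug-related toxicity, Protocol 6.6.2 says "the study drug judged by the investigator to have caused the toxicity should be discontinued" and the other drug continued. Temporary interruption and permanent discontinuation are separate AE actions (Protocol 8.1). If the entry stays at the first, the exception does not apply.

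**When the rule operates.** SAP 5.4.2 places the primary analysis about 12 months after the last enrolment. Twelve cycles take 12 × 28 = 336 days, and 336 / 30.4375 = 11.0 months (month length from SAP 6.6). The schedule of assessments allows up to 2 weeks plus 2 days before Cycle 13: 336 + 16 = 352 days, and 352 / 30.4375 = 11.6 months. Without cycle delays, nearly every patient still on MOR00208 at that cut would have reached Cycle 13, so the rule would supply the LEN reason for nearly all of them. SAP 5.4.3 runs the final analysis once all patients have had their EOT visit, so the rule should then have nobody left to act on.

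**Where the label goes.** It feeds the LEN discontinuation reasons in SAP 8.2. That section also tabulates, with reasons, patients who stopped LEN before completing 12 cycles; an early stopper could appear there beside the reason *As per protocol*, which is contradictory. SAP 20.5.3 ignores LEN stops made as per protocol when summarising time to dose reduction or discontinuation. If the label is reused there, early stops drop out.

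**Size.** SAP 8.2 percentages are of enrolled patients. With the planned 80, one patient is 1/80 = 1.25 percentage points. The documents give no count of affected patients.

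**The case against.** The strongest reply is that the rule sets only a reason.

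- **Completion.** SAP 8.2 defines successful completion as 12 cycles on both drugs. It counts early discontinuations by timing, and it splits patients reaching Cycle 13 by the drug they are on. None of these definitions depends on the label. This stands.
- **LEN tolerability.** Other planned outputs do not use the label: AEs leading to LEN discontinuation or other action (SAP 10.7.3), dose reductions and interruptions (8.9.3, 8.9.4), dose intensity (16.2, 17.7) and exposure split at the actual LEN stop (16.5.1, 20.11.3). This also stands.
- **Toxicity stops.** These are what the AE exception is built to catch. The toxicity route fails only if the site leaves the AE action at interruption. That narrows this route but leaves progression and the other non-AE reasons untouched.
- **Missing text.** Most of SAP 21.3, on LEN discontinuation at completion of Cycle 12, is absent from the text available for review. The change log for Addendum 6.0 describes only extended search terms, so nothing available shows that the rule was replaced. The full section should be checked.

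A reader might infer that early stoppers are counted as completers, or that LEN intolerance is understated across the report. The documents do not support either inference, for the reasons in the first two items.

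**Conclusion.** The point holds as a gap in how reasons are assigned. Read as written, SAP 8.2 reports a wrong LEN stop reason for patients who stopped LEN before completing 12 cycles, stayed on MOR00208 to Cycle 13, have no EOT page, and have no AE marked as permanent discontinuation. It affects the reported reasons at the primary analysis and other cuts with MOR00208 ongoing, and possibly the SAP 20.5.3 summaries.

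It does not affect ORR or the count of patients completing 12 cycles on both drugs, and should not affect the final analysis. The total effect cannot be estimated from the documents; it is 1.25 percentage points per patient if 80 are enrolled. The conclusion assumes that the missing part of SAP 21.3 does not add a dose-date check.

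**What to change.** Assign *As per protocol* only when the Lenalidomide Dosing Record shows that the patient reached the end of the planned 12 LEN cycles without an earlier permanent stop. Handle separately a Cycle 12 dose withheld through a temporary interruption, so that it is not counted automatically as an early discontinuation.

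Otherwise report an early LEN discontinuation, with the reason set as follows:

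- *Adverse event*, if an AE record shows LEN permanently discontinued, or interrupted and never restarted with no intervening progression or other recorded reason.
- *Disease progression*, if LEN stopped at documented progression.
- Otherwise the recorded reason or, where there is none, *Other/unknown*.

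The condition on intervening progression prevents every unresumed interruption from being attributed to an AE. Apply the same date check to free-text EOT entries mapped to *As per protocol*, such as COMPLETED, and state in SAP 20.5.3 that it uses the checked label.

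The cost is one extra derivation step on data already collected, and possibly fewer patients in the *As per protocol* row.
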